5.0 Study Procedures

All the erector spinae plane blocks will be placed preoperatively after sedation, before intubation and prior to surgery. All procedures will be done using sterile technique with masks, hats, and sterile gloves. All procedures will be placed under the supervision of the attending anesthesiologist on the acute pain service or the attending anesthesiologist in the VATS room.

To perform the ESP block, an ultrasound probe is used to visualize the ES musculature about 3 cm laterally from the T5 spinous process. In a cephalad-to-caudad direction advance the needle and inject the anesthetic in the interfacial plane deep to the ES muscles. Confirm positioning by visualization of needle tip and elevation of ES muscles off the transverse process with anesthetic injection. Surgeon infiltration is performed intraoperatively under direct thoracoscopic guidance. The intercostal space will be visualized and injected with LB. Typically, T4 through T8 are infiltrated with 2-3mL of the anesthetic mixture.

All patients will receive 1gm of acetaminophen and 600mg of gabapentin preoperatively. Patients above 70yo will receive 300mg of gabapentin. General anesthesia will be induced in the operating room and the patient will be placed in the lateral position for the VATS procedure. All patients will

receive intraoperative lidocaine and ketamine which is used to decrease opioid use after surgery and is being used as part of ERAS protocol. The patients will be intubated with dual lumen endotracheal tubes and placed on one-lung ventilation for the procedure. All patients will receive intravenous patient-controlled analgesia (PCA hydromorphone) post-operatively for breakthrough pain. They will also be scheduled on PO acetaminophen. PO oxycodone PRN will be started on POD 1 once patients tolerate diet.

Opioid usage at 1,24,48,72 hours after the block will be recorded by a member of the research team. Pain scores at rest and on movement (knee flexion) will be measured by the investigator using Visual Analog Scale (VAS). Nausea will be measured using a categorical scoring system (none=0; mild=1; moderate=2; severe=3). Sedation scores will also be assessed by a member of the study team using a sedation scale (awake and alert=0; quietly awake=1; asleep but easily roused=2; deep sleep=3). All these parameters will be measured at 1, 24, 48 and 72 hours after the epidural or PVB. Patients will be encouraged to ambulate on postoperative day 1 under supervision.

All patients will receive a phone call 6 months after surgery for assessment for chronic postsurgical pain. Patients will be assessed by a member of the research team over the phone. They will be assessed on their pain score and narcotic usage by using the Brief Pain Inventory. Study participation will conclude after the 6 month follow questionnaire has been completed.

6.0 Reporting of Adverse Events or Unanticipated Problems involving Risk to Participants or Others

Patients will be monitored by the primary team during the postoperative period which is after surgery, through hours, 24, 48, and 72. We will also follow up in 6 months with a telephone call to complete a questionnaire which will conclude all study participation. Any adverse events or unanticipated problems that are reported to the acute pain anesthesia resident who is not listed on the study will contact the Principal investigator or one of the study personnel and all events will be addressed immediately. All adverse events or unanticipated problems that meet the criteria for prompt reporting will be reported to the IRB within 5 business days.

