1.0 Background

Video-assisted thoracic surgery (VATS) is being performed more frequently due to its less invasive nature, decreased postoperative pain, and shortened post-operative hospital stay. However, VATS procedure still results in significant postoperative pain and the ideal analgesic for postoperative pain control following VATS remains unclear. Many modalities for pain control have been addressed in the literature: NSAIDs, opioids, epidurals, paravertebral blocks, and surgeon infiltration (1, 2). These have been used to manage the significant postoperative pain from VATS procedures remains to be codified and changes based on provider preference. The purpose of this study is to determine the effectiveness of Erector Spinae Plane Block (ESP) versus surgeon infiltration for postoperative analgesic control after VATS.

Erector Spinae Plane block was first described by Forero in 2016. This block has shown promise in relieving neuropathic pain and in providing analgesic coverage in laparoscopic cholecystectomy, mastectomy, and thoracic surgeries (3-7). This block can be thought of as a modified paravertebral block, and shows promise of increased safety compared to the paravertebral block. This is due to the unique anatomical approach that allows for anesthetic infiltration of the dorsal rami without the risk of needle insertion into the paravertebral space (6). The improved safety of this approach could allow this block to be used on higher risk patients, like those who present with coagulopathies.

Another common method of managing postoperative VATS pain is through surgeon infiltration of the intercostal space with local anesthetic. To perform infiltration, surgeons inject the anesthetic with direct visualization of the intercostal space, providing targeted analgesic coverage to the affected area (8). Some drawbacks to this process are the relatively short duration of action of the block, and the requirement of the surgeon to inject all affected intercostal spaces to achieve the desired dermatomal block(1, 2).

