2.0 Rationale and Specific Aims

The specific aim of the study is to compare the difference between the ESP block and surgeon infiltration in achieving the following:

- 1. Improved postoperative pain scores
- 2. Decreased opioid requirements
- 3. Improved patient satisfaction scores
- 4. Decreased opioid side effects (Nausea, sedation, ileus, urinary retention, respiratory depression)

The primary endpoint of this study will be VAS pain score. The VAS scores will be taken with both rest and movement.

The secondary endpoint includes intravenous opioid consumption and opioid side effects (nausea, sedation, ileus, urinary retention, respiratory depression). The IV and PO opioid doses will be quantified at 1, 24, 48, and 72 hours. We will also measure postoperative nausea and sedation scores at 1, 24, 48, and 72 hours. We will measure time to first flatus, incidence of urinary retention, incidence of respiratory depression, and time to discharge.

All patients will receive a phone survey 6 months after surgery to assess for pain and quality of life.

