4.0 Enrollment/Randomization

All VATS cases scheduled by thoracic surgeons at IU Health University Hospital will be identified. The subjects will be contacted initially face-to-face by either [name] or [name] in their clinics prior to their scheduled surgery date. They will be given a copy of the consent and authorization form explaining this study. The subjects will again be contacted face to face in POCU on the day of surgery and the study will be explained in detail and all questions will be answered. If participation is agreed, written consent will be taken and a signed copy of both the authorization and consent will be given to the participant.

A total of 120 subjects will be randomized by the computer program Research Randomizer into three groups (40 per group): The primary investigator will inform the anesthesiologist who will be doing the block as to what group the patients are randomized to. The research staff completing the patients assessments will be the only person blinded to the randomization.

- 1. Ultrasound guided LB Erector Spinae Plane Block with 20ml of Exparel® and 10ml 0.25% bupivacaine
- 2. Ultrasound guided SB Erector Spinae Plane Block with 30ml 0.5% bupivacaine
- 3. Surgeon Infiltration under video guidance with 20ml of Exparel® and 10ml of 0.25% bupivacaine

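### Section 4.0 assigns the infiltration group 30 ml of mixture, Section 5.0 gives 2-3 mL for T4 to T8 on an unstated basis, and the plan does not reconcile the two

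*Combined protocol and SAP*

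**What the plan says.** Section 4.0 defines the third randomized group as "Surgeon Infiltration under video guidance with 20ml of Exparel® and 10ml of 0.25% bupivacaine". The first group is defined with the same components: "Ultrasound guided LB Erector Spinae Plane Block with 20ml of Exparel® and 10ml 0.25% bupivacaine". Group 2 receives a block with standard bupivacaine only, so groups 1 and 3 form the one block-versus-infiltration pair with the same assigned mixture.

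Section 5.0 describes the infiltration technique and puts the amount this way: "Typically, T4 through T8 are infiltrated with 2-3mL of the anesthetic mixture". The unit of measure is given (mL). The basis is not: the sentence could mean each intercostal space, each injection, or the whole procedure. Section 5.0 names no injection site other than the intercostal spaces. No section says that the 30 ml is a prepared quantity of which only part is used, or what becomes of any remainder.

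The data listed in Sections 5.0 and 8.0 cover opioid use, pain, nausea, sedation, satisfaction and clinical events. The volume injected is not among them.

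**The concern.** The trial's stated aim is to "compare the difference between the ESP block and surgeon infiltration", and the first part of the primary hypothesis in Section 8.0 is that the block gives lower pain scores. Because groups 1 and 3 are assigned the same mixture, a reader will take the contrast between them as a comparison of two ways of delivering the same drug quantity.

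That holds only if group 3 receives what Section 4.0 assigns. A surgeon who follows Section 5.0 and reads the amount as per space would give one third to one half of it. The contrast would then carry a difference in drug quantity as well as in technique. On the assumption that less drug does not give better analgesia, the imbalance would favour the trial's own hypothesis. Without a stated or recorded volume, the report could not say what the infiltration arm consisted of.

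**Working it through.** **Inputs**
- Group 3 components, Section 4.0: 20 ml and 10 ml.
- Group 1 components, Section 4.0: 20 ml and 10 ml.
- Amount in the technique description, Section 5.0: 2 to 3 mL.
- Levels, Section 5.0: T4, T5, T6, T7, T8, which is 5.

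**Assigned volume.** The plan gives the components, not the sum: 20 + 10 = 30 ml for group 3, and the same for group 1.

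**Volume implied by Section 5.0 on each reading**

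| Reading of 2-3 mL | Arithmetic | Volume | Share of 30 ml | Remainder |
|---|---|---|---|---|
| Per space, one injection at each of five levels | 5 × 2 to 5 × 3 | 10-15 ml | 10/30 = 33% to 15/30 = 50% | 30 − 10 = 20 ml to 30 − 15 = 15 ml |
| Total for the procedure | 2 to 3 | 2-3 ml | 2/30 = 7% to 3/30 = 10% | 28 ml to 27 ml |
| Per injection, number of injections not stated | 2 or 3 × number of injections | not determined | not determined | not determined |

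**What it takes to reach 30 ml**
- In equal amounts over five levels: 30/5 = 6 ml per level, which is 6/3 = 2 to 6/2 = 3 times the amount in Section 5.0.
- At the stated amount per injection: 30/3 = 10 to 30/2 = 15 injections. Within five levels that is 10/5 = 2 to 15/5 = 3 injections per level; otherwise further sites are needed.

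**Other ways of counting**
- Four gaps between T4 and T8 instead of five levels: 4 × 2 = 8 to 4 × 3 = 12 ml, further from 30 ml.
- Five levels on both sides: 10 × 2 = 20 to 10 × 3 = 30 ml. This meets the assigned volume only at its upper end, and the documents do not describe infiltration on both sides.

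So the two sections agree only if there are repeat injections or additional sites, and Section 5.0 describes neither. The documents give no relation between volume and VAS score, so the possible effect on the pain comparison cannot be computed from them.

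**The case against.** The best defence is that the two sections do different jobs. Section 4.0 sets the quantities for all three groups. Section 5.0 describes technique, and for the block it states no volume at all, so the reader must take that from Section 4.0. Infiltration can be read the same way, with Section 5.0 giving only the usual distribution. Its sentence is qualified by *typically* and sets no cap. Section 1.0 also refers to "the requirement of the surgeon to inject all affected intercostal spaces to achieve the desired dermatomal block", so T4 to T8 need not be the limit. With two or three injections per level, the full 30 ml is used and no imbalance arises.

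Much of this stands. A reader might infer that group 3 will be given less than its assigned quantity. The documents do not support that: the 33-50% figure needs a per-space basis, one injection per space, and no spaces beyond T4 to T8. Nor can a reader infer that the volume goes unrecorded. The data form is not among the documents, and operative notes may hold it.

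A reader might also infer that equal volumes would make group 1 versus group 3 a pure test of technique. They would not. "All the erector spinae plane blocks will be placed preoperatively after sedation, before intubation and prior to surgery", whereas "Surgeon infiltration is performed intraoperatively under direct thoracoscopic guidance". Operators differ too: Section 4.0 refers to "the anesthesiologist who will be doing the block", while the surgeon does the infiltration. Comparing the two strategies as delivered remains legitimate and fits the aim in Section 2.0.

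The defence does not remove the gap in the text. A descriptive sentence that, on the per-space reading, differs two- to threefold from the assignment of a randomized arm still has to be squared with it. Comparing strategies as delivered also requires knowing what was delivered.

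**Conclusion.** The point holds as an unreconciled difference between two stated quantities for one randomized arm. Confidence in that is high: both sentences are complete, the arithmetic is simple, and no other section connects them.

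Its size depends on the reading: 10-15 ml (33-50% of 30 ml) per space, 2-3 ml (7-10%) in total, or no shortfall with 10-15 injections of 2-3 ml. An actual imbalance between groups 1 and 3 is possible and not demonstrated. If there is one, drug quantity is added to timing and operator as a difference between those groups. Unlike those two, it need not be part of comparing the techniques. Group 1 versus group 2 is unaffected, because both are blocks whose volumes come from Section 4.0 alone.

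This should be fixed, because the text defines the comparator in the main contrast and the correction is cheap.

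**What to change.** The investigators should reconcile Sections 4.0 and 5.0 so that both give the same total volume for group 3, the basis of the 2-3 mL (per space, per injection or in total), and what happens to any remainder. Which figure is right is for them to say.

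The volume actually injected should be recorded for each patient in groups 1 and 3 and summarised by group. If a field for it already exists, the protocol should name it. Because injected volume arises after randomization, it belongs in the report as a description of treatment delivered, not as an adjustment in the primary model.

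The cost is a wording change in two sections and at most one data field. Sample size and the planned analysis are unchanged.

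### Opioid given during surgery has no rule, data item or interval of its own, although ESP precedes surgery and infiltration does not, so the opioid comparison (Aim 2) is unequal or incomplete on either reading of the clock

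*Combined protocol and SAP*

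**What the plan says.** All references are to the combined protocol and SAP.

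- **Timing of treatment (Section 5.0).** For groups 1 and 2: "All the erector spinae plane blocks will be placed preoperatively after sedation, before intubation and prior to surgery". For group 3: "Surgeon infiltration is performed intraoperatively under direct thoracoscopic guidance". No point within the operation is given for the infiltration.
- **Drugs named (Section 5.0).** Acetaminophen and gabapentin are given before surgery. During surgery, all patients "receive intraoperative lidocaine and ketamine which is used to decrease opioid use after surgery". Afterwards: "All patients will receive intravenous patient-controlled analgesia (PCA hydromorphone) post-operatively for breakthrough pain", with scheduled acetaminophen and, from postoperative day 1, oxycodone as needed. Opioid during the operation is not mentioned.
- **Opioid readings.** Section 5.0: "Opioid usage at 1,24,48,72 hours after the block will be recorded by a member of the research team". Section 2.0: "The IV and PO opioid doses will be quantified at 1, 24, 48, and 72 hours", with no time zero. Section 8.0 lists the same four hours as a secondary outcome, analysed by repeated measures ANOVA, with no intraoperative variable.
- **Clock for the scores (Section 5.0).** The closing sentence on measurement times counts from an epidural or a paravertebral block. Neither is a study arm.
- **Aim 2 (Section 2.0).** "Decreased opioid requirements", ESP against infiltration.
- **Blinding.** Under Section 4.0 only the staff who assess patients are blinded. Under Section 5.0 the supervisor of the block may be the acute pain attending "or the attending anesthesiologist in the VATS room".

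**The concern.** By design the arms are treated differently during the operation. ESP patients have a block from the outset; group 3 has none until the surgeon injects. Opioid given in that phase could therefore differ between arms, and it is given by clinicians who may know the allocation. The plan neither governs that opioid nor gives it an interval of its own.

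Two things are at stake, both secondary. First, Aim 2: the opioid comparison either counts the operation differently by arm or leaves it out. Second, the 1 h VAS, nausea and sedation scores: opioid given shortly before can affect all three, and the planned data would not show how much each arm had received.

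**Working it through.** The plan gives no opioid mean, SD or operating time. Its only power figure (91%) is for VAS, so there is no opioid figure to reproduce and the point does not depend on that one. The check is a reading of the clock, followed by an illustration.

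**1. What each clock counts**

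| Opioid given | Literal clock, ESP | Literal clock, group 3 (infiltration taken as its block) | Common postoperative clock, all arms |
|---|---|---|---|
| At induction | counted | not counted | not counted |
| In surgery, before infiltration | counted | not counted | not counted |
| In surgery, after infiltration | counted | counted | not counted |
| After surgery | counted | counted | counted |

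The induction row follows from the ESP block preceding intubation and infiltration being intraoperative. The literal clock is unequal between arms. The postoperative clock is equal but has no reading for the operation.

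**2. Size of the clock difference (assumed times, not in the documents)**

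Assume ESP is placed s = 0.5 to 1 h before incision and surgery lasts D = 1 to 4 h.

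- ESP, postoperative hours in the 0–24 h window: 24 − (s + D). This runs from 24 − 1.5 = 22.5 down to 24 − 5 = 19. The window also holds all D hours of surgery.
- Infiltration at the end of surgery: 24 postoperative hours and no surgery.
- Infiltration at the start of surgery: 24 − D, that is 23 down to 20. The gap to ESP is then only s, 0.5 to 1 h, and both windows include the operation.
- First hour after an ESP block: s + D is at least 1.5 h, so it holds no postoperative time. For infiltration at the end of surgery, the first hour is wholly postoperative.

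**3. Illustration on a postoperative clock (assumed effects)**

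Noncentral t, n = 40 per arm (Section 4.0), two-sided 5% (Section 8.0), df = 78, critical t = 1.991, noncentrality d × √(40/2). Assume a true difference in total opioid of d = 0.63 SD.

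| Share of saving arising in surgery | d for postoperative opioid, same SD as total | Noncentrality | Power |
|---|---|---|---|
| none | 0.63 | 2.82 | 79.5% |
| 25% | 0.75 × 0.63 = 0.4725 | 2.11 | 55.1% |
| 50% | 0.50 × 0.63 = 0.315 | 1.41 | 28.5% |

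The equal-SD assumption matters. If intraoperative opioid is independent of postoperative opioid and carries 25% or 50% of the total variance (the same share as of the saving), the postoperative SD shrinks:

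- 25%: d = 0.4725 / √0.75 = 0.546, power 67%.
- 50%: d = 0.315 / √0.50 = 0.445, power 50%.

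The reverse also holds. If no saving arises in surgery and postoperative opioid has d = 0.63, adding an independent intraoperative part with those variance shares gives the total d = 0.63 × √0.75 = 0.546 (67%) or 0.63 × √0.50 = 0.445 (50%). The total can thus be the noisier outcome.

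**The case against.** The strongest reply has five parts.

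- **Unequal opioid exposure is inferred.** This stands. A reader might infer from the timing and the lack of blinding that group 3 will receive more opioid during surgery. No passage says so. Infiltration may come early, and the ERAS protocol mentioned in Section 5.0 may limit opioid, though the documents give no such rule. Even if it does, a dosing rule would not create a trial data item.
- **A saving during surgery is not simply lost.** This stands for the plan as written: counted from the block, opioid given in surgery falls inside the ESP windows. The loss arises only on a postoperative clock, which the plan does not state. But the literal clock has its own fault, the inequality in the table.
- **Postoperative opioid is a legitimate target.** This stands in part. Section 1.0 frames the purpose as postoperative analgesia. Aim 2, however, is not limited to the postoperative period, and the literal clock does not deliver a postoperative total either.
- **The 1 h scores are not biased.** This largely stands. A reader might infer that early pain is biased against ESP and early side effects in its favour. More opioid because no block is yet working would be a consequence of the assigned treatment, so 1 h remains a randomized comparison of strategies, once measured on a common clock. What suffers is interpretation, and recording the opioid helps only with that.
- **The data are recoverable from the anesthesia record.** Probably true, and it is why the fix is cheap. It does not make the interval a prespecified outcome.

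**Conclusion.** The point holds as a gap in the opioid outcome that should be closed; it does not threaten the primary analysis. That the plan has no rule, data item or interval for intraoperative opioid is plain from Sections 2.0, 5.0 and 8.0, as is the difference in treatment timing. It follows that Aim 2 is compared unequally on the literal clock (taking infiltration as group 3's block) or incompletely on a common postoperative one.

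The direction and size of any difference in intraoperative opioid are unknown. The power figures are not an estimate of loss in this trial: they run from no loss (79.5%) to 28.5% according to assumed shares and SDs that have no source in the documents. The effect on VAS at 24 and 48 h is expected to be small, which is a judgement rather than a calculation.

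**What to change.** **Section 5.0.** Add text such as: *For every patient, all opioid given from induction to the end of surgery is taken from the anesthesia record and entered as a separate interval. Intraoperative and postoperative opioid are expressed in one stated opioid-equivalent unit. Postoperative intervals in all three groups start from one common time zero.* The sponsor should name that time zero (end of surgery is one candidate) and reconcile the two clocks now in the section, one counted from the block and one from an epidural or paravertebral block. The unit has to be stated because morphine equivalents appear only in the home-dose exclusion in Section 3.0.

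**Section 8.0.** Report intraoperative opioid by group. Add total opioid (intraoperative plus postoperative) as a secondary outcome for Aim 2, beside the postoperative outcome and not in place of it. Do not adjust for intraoperative opioid as a covariate: it arises after randomization and may be part of the treatment effect.

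**Cost.** One REDCap field from a record that should already exist, and one more secondary outcome. The total may be noisier than postoperative opioid alone if no saving arises during surgery, which is the reason to keep both. No dose or clinical rule changes.

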8.0 Statistical Considerations

Primary outcome: VAS score at 24 and 48 hours

Primary Research Hypothesis: ESP will provide lower pain scores compared to surgeon infiltration and ESP with LB will provide longer pain control than ESP with SB.

Secondary outcomes: Opioid usage after 1, 24, 48 and 72 hours. Pain scores using VAS at rest and on movement at 1, 24, 48 and 72 hours. Patient satisfaction scores at 24 and 48 hours. Nausea

scores at 1, 24, 48 and 72 hours. Sedation scores at 1, 24, 48 and 72 hours. Time to first bowel movement, incidence of urinary retention, and incidence of respiratory depression will be recorded as well.

Secondary Research Hypotheses: ESP blocks will show improved pain control, improved patient satisfaction scores, and decreased nausea and sedation scores compared to surgeon infiltration. Statistical analysis will be performed using a standard statistical program (SAS or SPSS). All data will be summarized (means, standard deviations, standard errors, and ranges for continuous variables; frequencies and percentages for categorical variables) by group. Demographic data will be compared between the three groups using ANOVA or chi-square tests as appropriate. The primary outcome, VAS at 24 and 48 hours, will be compared between the groups using repeated measures ANOVA; the model will include fixed effects for group, time, and the group by time interaction and random effects to allow correlations between the two times and different variances for the two times. Pain and satisfaction scores and opioid usage over time will be analyzed using repeated measures ANOVA. Nausea and sedation scores will be compared between groups at each time point using Mantel-Haenszel chi-square tests for ordered categorical data. Distributions of the continuous variables will be examined, and a transformation of the data (e.g. natural logarithm) or nonparametric tests will be used as necessary. A 5% significance level will be used for all comparisons.

Based on prior studies, the coefficient of variation for the VAS score at 24 and 48 hours is estimated to be 0.70. With a sample size of 40 per group, the study will have 91% power be able to detect a 60% decrease in VAS score between any two groups, assuming two-sided tests each conducted at a 5% significance level.

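### Movement VAS is scored on knee flexion alone, which does not directly load the treated chest wall and may miss differences in movement-evoked pain

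*Combined protocol and SAP*

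**What the plan says.** Section 5.0 defines the movement score in a parenthesis: "Pain scores at rest and on movement (knee flexion) will be measured by the investigator using Visual Analog Scale (VAS". This is the only movement the document ties to a pain score. Supervised walking on the first postoperative day is encouraged in the same section, but no VAS reading is linked to it. Cough, deep breathing and trunk or arm movement are not mentioned for any score, and no reason is given for choosing the knee.

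The treatments act elsewhere. For the ESP block, "an ultrasound probe is used to visualize the ES musculature about 3 cm laterally from the T5 spinous process". For surgeon infiltration, "Typically, T4 through T8 are infiltrated with 2-3mL of the anesthetic mixture".

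On the role of the score, Section 2.0 names VAS as the primary endpoint and adds: "The VAS scores will be taken with both rest and movement". Section 8.0 gives "Primary outcome: VAS score at 24 and 48 hours", without saying rest or movement, and then lists among the secondary outcomes "Pain scores using VAS at rest and on movement at 1, 24, 48 and 72 hours".

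**The concern.** A movement score is useful in an analgesia trial when the movement provokes the pain that the treatment is meant to relieve. Here the surgical field and the analgesic techniques are thoracic and the movement is of the leg. If the manoeuvre provokes little chest-wall pain, the score has little to separate the arms with.

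What is at stake is the reading of a null result. If movement VAS does not differ between ESP and infiltration, or between liposomal and standard bupivacaine, two explanations remain: the techniques relieve movement-evoked chest-wall pain equally, or the stimulus did not test it. The plan collects nothing else on movement that would tell these apart.

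**Working it through.** The plan gives no figure for how knee flexion performs after VATS, so there is none to reproduce. Its power statement (40 per group, CV 0.70, 91%) does not say whether it concerns rest or movement VAS, and this point does not rest on it.

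**Step 1. Match of stimulus to target.**

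| Item | Location or content | Source |
|---|---|---|
| Surgery | Thoracoscopic (VATS) | Section 3.0 |
| ESP block | About 3 cm lateral to T5 | Section 5.0 |
| Infiltration | Typically T4 to T8 | Section 5.0 |
| Manoeuvre for movement VAS | Knee flexion | Section 5.0 |
| Other manoeuvre for VAS | None | Whole document |
| Reason for knee flexion | None | Whole document |

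The rows are documented. The step from them to reduced sensitivity is anatomical inference: knee flexion does not directly load the T4 to T8 region, although some indirect trunk movement is possible. The word the evidence supports is *may*.

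**Step 2. Outcomes reached.**

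- Secondary movement VAS at 1, 24, 48 and 72 hours (Section 8.0): affected.
- Primary VAS at 24 and 48 hours: affected if movement VAS is part of it, as Section 2.0 can be read. Not affected if it is rest VAS only. Section 8.0 does not settle this.
- Rest VAS and opioid use: not affected.

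**Step 3. Can the paired rest score rescue the movement score?** Let d = movement VAS minus rest VAS for one patient at one time point, scaled so that mean VAS = 1. Assumptions: the CV of 0.70 in Section 8.0 applies to both scores; the two means are equal (knee flexion adds no pain); and the rest-movement correlation r, which is not in the documents, is 0.5, 0.7 or 0.9.

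SD(d) = 0.70 × √(2(1 − r)), and the 95% half-width = t × SD(d)/√n, with t = 1.980 for n = 120 and 2.023 for n = 40.

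| r | SD(d) | Half-width, n = 120 | Half-width, one arm of 40 |
|---|---|---|---|
| 0.5 | 0.700 | 0.127 | 0.224 |
| 0.7 | 0.542 | 0.098 | 0.173 |
| 0.9 | 0.313 | 0.057 | 0.100 |

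These are precisions. A true rise equal to the half-width would be detected only about half the time. For 80% power the half-width is multiplied by about 2.80/1.96 = 1.43, so with all 120 patients the detectable rise is about 18%, 14% or 8% of mean VAS (0.127, 0.098 and 0.057 × 1.43).

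The paired data could therefore indicate whether knee flexion raised pain by an amount of that order. They cannot show what a chest-wall manoeuvre would have shown, and they do not measure lost sensitivity between arms.

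**The case against.** The strongest case against is that the defect is inferred. Nothing in the documents shows how knee flexion behaves after VATS, indirect trunk movement could provoke some chest pain, and the sponsor may have a reason it did not write down. This stands, and it limits the claim to *may be insensitive*. If there is a reason, Section 5.0 should give it. It is also true that rest VAS and opioid use remain as sound comparisons of the arms.

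Four stronger readings are tempting, and the documents support none of them.

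- **That the movement score is in effect a second rest score.** This would need data on movement minus rest, and there are none.
- **That the trial loses a stated amount of power.** Any such figure needs an attenuation factor, and the documents supply none.
- **That knee flexion was carried over from another protocol.** The same paragraph says "All these parameters will be measured at 1, 24, 48 and 72 hours after the epidural or PVB", and neither technique is a study arm. That timing reference needs correcting on its own account. It does not show where knee flexion came from, and the same paragraph also times opioid use from the block.
- **That blinded assessment rules out bias in this score.** Section 4.0 says "The research staff completing the patients assessments will be the only person blinded to the randomization", but Section 5.0 has VAS measured by the investigator, and Section 4.0 has the primary investigator pass on the allocation. Who scores VAS, and whether blinded, is not settled. The statement that this point concerns sensitivity rests only on the manoeuvre being the same in every arm.

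**Conclusion.** The point holds as a design comment that should be acted on, with medium confidence. The plan's only movement for pain scoring does not directly load the region being treated, no reason is given, and a null result on movement VAS would be ambiguous. The certain reach is one secondary outcome at four time points. The reach to the primary outcome depends on whether it includes movement VAS.

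The size of the lost signal is unknown and none is claimed. The conclusion rests on anatomical inference from the sites named in Section 5.0. The detectable-rise figures of about 8% to 18% describe only what the paired rest score could reveal, under an assumed correlation of 0.5 to 0.9, and do not bear on how serious the point is.

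**What to change.** **Before the first patient.** In Section 5.0 and on the data form, replace knee flexion with one standardised chest-wall manoeuvre, for example a voluntary cough or maximal deep inspiration. Use that score wherever Sections 2.0 and 8.0 refer to movement. Cost: small edits to Sections 2.0, 5.0 and 8.0 and one field on the form. The four existing assessments suffice, so no visit is added.

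**If enrolment has begun.** Section 10.0 gives a start in late 2018, and the documents do not say how far recruitment has gone. In that case keep knee flexion, add the chest-wall score as a separately labelled item at the four existing assessments, do not pool the two, and report the existing score as *VAS on knee flexion*. Cost: the same small edits, plus one extra score at each of four assessments for each remaining patient. The drawback is that the new score would cover fewer than 40 patients per arm, so its comparison between arms would be less precise.
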